10. INDEPENDENT SAFETY COMMITTEES

Medical Reviewer

The role of the Medical Reviewer is to adjudicate pre-specified adverse events in a consistent and unbiased manner throughout the course of the trial. The Medical Reviewer is an independent, qualified physician whose medical specialty may include anesthesiology. The Medical Reviewer will adjudicate serious adverse events that are possibly related to the surgical procedure or the Acumen™ Hypotension Prediction Index (HPI) Feature Software or death. The Medical Reviewer will notify the site or Sponsor if additional potential adverse events are identified during the adjudication process.

Data Safety Monitoring Board

An independent (4-Member) Data Safety Monitoring Board (DSMB) will be established to oversee the Trial outcome. Members of the DSMB must be free of significant conflicts of interest (e.g., Financial, intellectual, professional, or regulatory), or measures should be in place to minimize perceived conflict of interest. Members of the DSMB are also experts in all scientific disciplines needed to interpret the data and ensure Trial participant safety, including an independent biostatistician. The DSMB will meet via teleconference a minimum of semiannually or at least two (2) times over the course of the Trial. The DSMB manual of operation (MOP) will be maintained by the Sponsor as part of the clinical Trial project plan. The DSMB MOP will outline membership and voting procedures as well as DSMB Meeting documentation and communication. The DSMB meetings will include an open session where the Sponsor will present Trial updates, review trends for device malfunctions, protocol deviations and subject withdrawal reasons to communicate Trial progress. The Investigators may attend the open session.

In addition to the open portion of the DSMB meetings, there will be closed sessions that will only be attended by the DSMB members.

The DSMB will perform the following activities during the closed session of the meetings:

- Assess primary safety endpoint
- Assess participant risk versus benefit, performance of Trial sites, and other factors that can affect Trial safety outcome
- Review factors external to the Trial when interpreting the data, such as scientific or therapeutic developments that may have an impact on the safety of the participants or the ethics of the Trial
- Make recommendations to Edwards Lifesciences, IRB, and investigators concerning continuation or conclusion of the Trial based solely on safety evaluation
- Protect the confidentiality of the Trial data and the results of monitoring

To mitigate any potential release of Trial results, the analysis of safety endpoint will be led by the independent biostatistician serving on the DSMB. The biostatistician will have no contact with the Sponsor or any Trial sites. Furthermore, the identification of the other DSMB members will not be shared with the sites during the conduct of the Trial.

THIS DOCUMENT CONTAINS CONFIDENTIAL AND PROPRIETARY INFORMATION OF EDWARDS LIFESCIENCES, LLC. IT MAY NOT BE REPRODUCED OR DISCLOSED WITHOUT PRIOR WRITTEN PERMISSION FROM EDWARDS LIFESCIENCES, LLC.

Edwards Lifesciences, Edwards, the stylized E logo, HemoSphere, Acumen, Acumen IQ, FloTrac, and ForeSight Elite oximetry Sensor are trademarks of Edwards Lifesciences Corporation.

Stopping Rules

Continuation or discontinuation of the trial will be based upon the DSMB's evaluation of trial safety.

This study will be stopped prior to its completion if: (1) the intervention is associated with adverse events that call into question the safety of the intervention, (2) any new information becomes available during the trial that necessitates stopping the trial and/or (3) Based on the results of interim analysis.

THIS DOCUMENT CONTAINS CONFIDENTIAL AND PROPRIETARY INFORMATION OF EDWARDS LIFESCIENCES, LLC. IT MAY NOT BE REPRODUCED OR DISCLOSED WITHOUT PRIOR WRITTEN PERMISSION FROM EDWARDS LIFESCIENCES, LLC.
Edwards Lifesciences, Edwards, the stylized E logo, HemoSphere, Acumen, Acumen IQ, FloTrac, and ForeSight Elite oximetry Sensor are trademarks of Edwards Lifesciences Corporation.

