6. DATA AND ANALYSIS CONVENTIONS

6.1 General Conventions

The baseline characteristics and demographics, the medical history data of each study subject will be collected during the subject screening process and recorded on an electronic case report form (eCRF). The hemodynamic measurement data will be downloaded from HemoSphere advanced monitoring platform.

All endpoints will be presented using descriptive statistics by assigned treatment group; continuous variable will be summarized with the mean, standard deviation (SD), median, and interquartile range (IQR); binary and categorical variables will be presented using count and percentage.

Other summaries (e.g., minimum, maximum, standard error, 95% intervals, coefficient of variation (CV) or %CV, odd ratio) will be used as appropriate. Sample sizes shown with summary statistics are the number (n) of patients with non-missing values. All percentages should be rounded and reported to a single decimal place (xx.x%). If percentages are reported as integers, percentages greater than 0% but <1% will be reported as <1%, whereas percentages greater than 99% but <100% will be reported as >99%. A percentage of 100% will be reported as 100%.

For categorical endpoints, logistic regression and the approximate Z test will be performed on the primary outcomes and exploratory analysis. Summary statistics and p-values from the statistical comparison will be displayed in result report. The p-value will present with three decimals. P-values less than 0.001 will be reported as <0.001. Additionally, ad-hoc analyses may be conducted as deemed appropriate.

An independent Data Safety Monitoring Board (DSMB) will evaluate the data at interim.

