By the study designed parameter table in section 2.3 and the Z statistic calculated at each study stage with the trial data collected at present stage in addition to data collected in previous stage or stages, following judgement will be conducted for interim analysis and final analysis. For first and second interim analyses, if the calculated Z value is equal to or less than the critical Z value in the effectiveness boundary column, the null hypothesis will be rejected, and the study will stop for achieving the study objective; if the calculated Z statistic is greater than critical Z value for effectiveness but it is close to the critical value but could not reject null hypothesis, the study continues to next step, and the study sample seize will be reassessed by the principles of adapted group sequential study design. If it is necessary, more study subject will be enrolled for the purpose to achieve the study objectives. For final analysis, if the calculated Z statistic is equal to or less than the critical Z value listed in effectiveness boundary column, the null hypothesis will be rejected, and the alternative hypothesis will accept, the study objective is achieved, otherwise, the null hypothesis will accept, the study objective will be not achieved.

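### The DSMB's safety-only remit contradicts the interim effectiveness stop, its primary safety endpoint is undefined, and no action is tied to a boundary crossing in the harmful direction

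*Combined protocol and SAP*

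**What the plan says.** **DSMB remit.** Protocol section 10 has the DSMB make recommendations "concerning continuation or conclusion of the Trial based solely on safety evaluation". The Stopping Rules open in the same vein: "Continuation or discontinuation of the trial will be based upon the DSMB's evaluation of trial safety". They then list three grounds for stopping early: adverse events that cast doubt on safety, new information, and the results of interim analysis.

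**DSMB tasks.** The closed-session list begins "Assess primary safety endpoint". The next item is "Assess participant risk versus benefit, performance of Trial sites, and other factors that can affect Trial safety outcome". The section opens by saying that a "Data Safety Monitoring Board (DSMB) will be established to oversee the Trial outcome".

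**Interim analysis.** SAP 6.1 states: "An independent Data Safety Monitoring Board (DSMB) will evaluate the data at interim". SAP 8.1 says that when the limit is met at either interim, "the null hypothesis will be rejected, and the study will stop for achieving the study objective". The protocol's Randomization and Blinding section unblinds one independent biostatistician to run the interim and keeps all other parties blinded at that time.

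**Boundaries.** The protocol table (Planned Interim Analyses) gives upper and lower limits of ±2.96259, ±2.35898 and ±2.01404 at 50%, 75% and 100% information, all labelled as effectiveness limits, with futility limits of ±0.40273 and ±1.12741 at the interims. The SAP 2.3 table gives the three lower limits only.

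**Meetings.** "The DSMB will meet via teleconference a minimum of semiannually or at least two (2) times over the course of the Trial".

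**The concern.** The text that tells the DSMB what it may recommend on leaves out the one formal stopping criterion in the trial. The text that contains the criterion names nobody to recommend acting on it. If the first interim crossed the boundary, the DSMB, the independent biostatistician and the sponsor could each point to a sentence that makes the decision someone else's. That is best settled before the data exist.

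The harm side has a related gap. Death, myocardial injury, stroke, cardiac arrest, AKI and serious infection are the events a harmful strategy would raise, and they make up the effectiveness composite. The DSMB is directed to a safety endpoint that has no definition. No sentence tells it to look at the composite by arm, and no sentence says what a crossing in the wrong direction would mean.

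**Working it through.** **1. The remit, side by side**

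| Text | What it gives the DSMB |
|---|---|
| Protocol 10, recommendations | Continue or stop, on safety only |
| Protocol 10, Stopping Rules, lead sentence | Continuation rests on its safety evaluation |
| Protocol 10, Stopping Rules, third ground | Stop on interim results; no body named |
| SAP 6.1 | Evaluates the data at interim |
| SAP 8.1 | Stop on the effectiveness Z; no body named |

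The first two rows cannot both stand with the last three. The DSMB may look at the interim data but is barred from recommending on effectiveness.

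**2. The primary safety endpoint**

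The only primary endpoint in either document is the effectiveness composite (Protocol 3 and 7; SAP 3.1). SAP 9 summarises deaths and adverse events descriptively. The closed-session task therefore has no defined object.

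**3. Reproducing the critical values**

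The O'Brien-Fleming-type spending function is α(t) = 2{1 − Φ(z₁₋α/₂/√t)}, with one-sided α = 0.025. At t = 0.5, 2.2414/0.7071 = 3.170, so 0.001525 is spent and the limit is 2.96259. Solving the later looks with the correlated normal gives 2.35902 and 2.01408, against 2.35898 and 2.01404 printed. The one-sided p-values 0.00153, 0.00916 and 0.02200 also match. Mirrored, the same values serve the protocol's two-sided 0.05 design, so the protocol table does contain a limit in the harmful direction.

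**4. What that limit would detect**

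Inputs: control rate 0.31 and 1426/2 = 713 per arm (Protocol 7). With the 15% attrition stated in SAP 2.3, 713 × 0.85 ≈ 606 per arm. The relative risks above 1 are assumptions.

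For RR 1.25, p₁ = 0.31 × 1.25 = 0.3875.

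SE = √[(0.31×0.69 + 0.3875×0.6125)/713] = √[(0.2139 + 0.2373)/713] = 0.02516.

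θ = 0.0775/0.02516 = 3.08.

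The interim means are θ√0.5 = 2.178 and θ√0.75 = 2.668, with correlation √(0.5/0.75) = 0.816.

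First interim: 1 − Φ(2.96259 − 2.178) = 0.216. By the second interim (bivariate normal): 0.625.

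| Assumed RR | 713 per arm: first look | By second look | 606 per arm: first look | By second look |
|---|---|---|---|---|
| 1.00 | 0.15% | 0.97% | 0.15% | 0.97% |
| 1.10 | 1.9% | 10% | 1.6% | 8.9% |
| 1.25 | 22% | 62% | 17% | 54% |
| 1.33 | 46% | 88% | 37% | 81% |

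A non-binding harm guideline can only reduce the chance of a later claim of benefit, so it costs no efficacy alpha.

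**5. The sign of Z**

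SAP 8.1 defines Z as control minus treatment, then rejects when Z is at or below a negative limit. Take SAP 2.3's own first-interim counts, 111 control and 74 treatment, with 1426/4 ≈ 357 per arm. The proportions are 0.3109 and 0.2073, the unpooled SE is 0.03256, and Z = 0.1036/0.03256 = +3.18. That is the success case in the SAP's own table, yet it does not satisfy Z ≤ −2.96259. Read literally, the rule declares success when treatment is worse.

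**6. Meeting frequency**

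Twice a year over the stated 24 to 36 months is about 4 to 6 meetings. The alternative in the same sentence allows two.

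**The case against.** **A reader might infer that the DSMB has no remit for effectiveness.** The documents do not support that. SAP 6.1 has it evaluate interim data. Protocol 10 charges it with overseeing the trial outcome and weighing risk against benefit, and benefit cannot be weighed without effectiveness data. The remit is contradictory and unassigned, not absent. The DSMB manual was not supplied. The protocol says it covers membership, voting, documentation and communication, so it may help, but it should not have to overrule the protocol.

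**A reader might infer that an early success could not be acted on without unblinding the sponsor.** This is not supported either. Closed sessions are for members only, the DSMB issues recommendations, it must protect monitoring results, and its biostatistician has no contact with the sponsor. What is missing is a sentence routing the interim result into that closed session.

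**A reader might infer that a worse composite triggers nothing.** That goes too far. The protocol has upper limits and futility limits. SAP 10 declares no change from the protocol's analyses, so those limits cannot be treated as withdrawn. If futility means stopping unless benefit exceeds 0.40273, an assumed RR of 1.25 meets it at the first interim with probability Φ(2.178 + 0.403) = 99.5%. If it means stopping when |Z| is below 0.40273, the probability is about 3%. The protocol does not say which reading applies, and the SAP table omits futility. There are also qualitative stops: the adverse-event ground in section 10, and suspension for unacceptable risk in section 20. Deaths are reported as serious adverse events, and other components can be. However, Protocol 9 excludes from adverse events symptoms due to surgery or ICU admission, which could leave out some postoperative AKI or troponin-detected injury.

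**A worst-case count of patients is tempting.** Two meetings could fall at the two interims, after about 713 of 1426 subjects. But two is a floor, and no text ties the meetings to the interims. Nor would a full 713 or 356 subjects remain to be enrolled at an interim, because enrolment can continue during the 30-day follow-up.

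Leaving harm to the DSMB's judgement is a legitimate design choice. That does not excuse an undefined endpoint or a contradictory remit.

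**Conclusion.** The point holds as a conflict between stated rules and an undefined term, and is worth correcting before the first interim. It does not show that the trial lacks safety oversight or that the sponsor's blind must be broken.

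Three things stand without any assumption: safety-only recommendations cannot be squared with the interim effectiveness stop; the primary safety endpoint is undefined; and the protocol and SAP boundary tables differ, with neither assigning an action to a crossing in the harmful direction. The sign conflict in SAP 8.1 makes the last of these more pressing, because the DSMB cannot safely be pointed to boundaries whose direction is unclear.

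The size estimates rest on a control rate of 0.31, the planned sample size and assumed harm relative risks. At RR 1.25 an upper limit used as a guideline would flag harm by the second interim in 54% to 62% of trials, depending on attrition. Modest harm (RR 1.10) would usually go unflagged, so the guideline would supplement the DSMB's judgement, not replace it.

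**What to change.** 1. **First, reconcile the boundaries.** State one definition of Z and the direction that counts as benefit, and make SAP 8.1, the SAP 2.3 table and the protocol table agree. Say whether the futility limits apply and how they are read.
2. **Protocol 10, recommendations and Stopping Rules.** Replace the safety-only basis with safety and the interim boundaries. State that the independent biostatistician reports interim results only to the DSMB's closed session, and that the sponsor receives only a recommendation.
3. **Protocol 10, closed-session tasks.** Replace the undefined endpoint with the 30-day composite and all-cause death by arm. Use the protocol's printed upper limits (2.96259 and 2.35898, with positive meaning more events on treatment) as a non-binding harm guideline.
4. **Meetings.** Choose between the semiannual schedule and the two-meeting minimum, and state only one.

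Cost: wording changes in the protocol, SAP and DSMB manual; about two to four more teleconferences if the semiannual schedule is kept (4 to 6 against 2); and a false harm flag with probability 0.97% by the second interim under no effect, which the DSMB may override. No additional patients and no efficacy alpha.

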11. RECEIVING, STORAGE, AND RETURN OF DEVICES

Receipt of Device Supplies

A packing list will accompany all device shipments. This list will include the inventoried product with receipt date and investigator and/or designee signature.

Storage

The HemoSphere advanced monitoring platform and all Trial product(s) shall be stored in a secure and clean area complying with the storage instructions provided in the labeling.

Device Accountability

The Investigator and/or delegated-Trial personnel shall keep records documenting the receipt, use, return, and disposal of the devices. Only the Investigator, delegated-Trial Personnel and/or designee(s) (i.e., Assisting Clinician(s)) may use the devices. The Investigator will supervise the use of the devices in Trial subjects. The Trial site shall account for which system/device was used for which subject as well as for the return of the system/device.

Return of Devices

The Principal Investigator or designee is responsible for returning the unused product back to the Sponsor.

THIS DOCUMENT CONTAINS CONFIDENTIAL AND PROPRIETARY INFORMATION OF EDWARDS LIFESCIENCES, LLC. IT MAY NOT BE REPRODUCED OR DISCLOSED WITHOUT PRIOR WRITTEN PERMISSION FROM EDWARDS LIFESCIENCES, LLC.

Edwards Lifesciences, Edwards, the stylized E logo, HemoSphere, Acumen, Acumen IQ, FloTrac, and ForeSight Elite oximetry Sensor are trademarks of Edwards Lifesciences Corporation.

12. CONFIDENTIALITY AND PRIVACY

Information about Trial subjects will be kept confidential and managed according to the requirements of the Health Insurance Portability and Accountability Act of 1996 (HIPAA). Consistent with these regulations, a signed authorization will be obtained that informs each subject of the following:

- What protected health information (PHI) will be collected from subjects in this Trial
- Who will have access to that information and why
- Who will use or disclose that information
- The rights of a research subject to revoke their authorization for use of their PHI

No subject demographic data or medical information will be used or shared outside the Sponsor and site staff unless an unanticipated adverse device effect (UADE) is reported. If a UADE is reported, all efforts will be made to keep subject information confidential. The Sponsor is dedicated to maintaining the confidentiality and privacy of subjects who volunteer to participate in the Trial. The Trial Investigator and the Trial site personnel are responsible for maintaining confidentiality throughout the clinical Trial. The Sponsor and Sponsor designated Trial personnel will have access to the data collected. The hard copies of the source documentation are to be maintained in a secure area with limited access.

To protect subject confidentiality, the subject's name must not appear anywhere on CRFs, or supporting documentation removed from the site. All subject identifiers (e.g., social security number) will be obliterated from all photocopies of source documents that have been removed from the site. All Trial documents will identify the subject by a subject Trial identification number and Protocol number assigned by the Sponsor (if applicable).

In the event that a subject revokes authorization to collect or use PHI, the Investigator, by regulation, retains the ability to use all information collected prior to the revocation of subject authorization. For subjects that have revoked authorization to collect or use PHI, attempts should be made to obtain permission to collect at least vital status (i.e., that the subject is alive) at the end of their scheduled Trial period.

THIS DOCUMENT CONTAINS CONFIDENTIAL AND PROPRIETARY INFORMATION OF EDWARDS LIFESCIENCES, LLC. IT MAY NOT BE REPRODUCED OR DISCLOSED WITHOUT PRIOR WRITTEN PERMISSION FROM EDWARDS LIFESCIENCES, LLC.

13. DATA HANDLING AND RECORD KEEPING

Source

Source data are all information, original records of clinical findings, observations, or other activities in a Trial necessary for the reconstruction and evaluation of the Trial. Source data are contained in source documents. Examples of these original documents, and data records include: hospital records, clinical and office charts, laboratory notes, memoranda, subjects' diaries or evaluation checklists, pharmacy dispensing records, recorded data from automated instruments, copies or transcriptions certified after verification as being accurate and complete, microfiches, photographic negatives, microfilm or magnetic media, x-rays, subject files, source worksheets that have been certified as source, and records kept at the pharmacy, at the laboratories, and at medical-technical departments involved in the Trial.

Required data for this Trial are to be recorded in the subject's file and/or via eSource and/or on worksheets, certified as source, for source documentation and data verification. Some of the source documentation generated during the Trial may also be the electronic data from the Monitor, laboratory data, or printout from Radiometer and YSI. Data may also be entered directly onto the eCRF during the visit. Because of the potential for errors, inaccuracies, and illegibility in transcribing data onto eCRFs, the Investigator must permit inspection of source documents by the Sponsor, and inspection by local and regulatory authorities.

Data Entry Timelines

It is recommended that electronic case report forms (eCRFs) be completed within 24 hours of data availability, but not more than 10 working days after completion of assessments.

THIS DOCUMENT CONTAINS CONFIDENTIAL AND PROPRIETARY INFORMATION OF EDWARDS LIFESCIENCES, LLC. IT MAY NOT BE REPRODUCED OR DISCLOSED WITHOUT PRIOR WRITTEN PERMISSION FROM EDWARDS LIFESCIENCES, LLC.

Edwards Lifesciences, Edwards, the stylized E logo, HemoSphere, Acumen, Acumen IQ, FloTrac, and ForeSight Elite oximetry Sensor are trademarks of Edwards Lifesciences Corporation.

14. CHANGES TO THE PROTOCOL

Changes to the research covered by this protocol must be implemented by formal protocol amendment. All amendments to the protocol must be initiated by the Sponsor.

Protocol amendments must not be implemented without prior IRB approval. Documentation of amendment approval by the Investigator and IRB or IEC must be provided to the Sponsor or its authorized representative. When the change(s) involve only logistic or administrative aspects of the Trial, the IRB only needs to be notified.

THIS DOCUMENT CONTAINS CONFIDENTIAL AND PROPRIETARY INFORMATION OF EDWARDS LIFESCIENCES, LLC. IT MAY NOT BE REPRODUCED OR DISCLOSED WITHOUT PRIOR WRITTEN PERMISSION FROM EDWARDS LIFESCIENCES, LLC.

Edwards Lifesciences, Edwards, the stylized E logo, HemoSphere, Acumen, Acumen IQ, FloTrac, and ForeSight Elite oximetry Sensor are trademarks of Edwards Lifesciences Corporation.

